14.5 Return of Genetic Testing Research Results

Results of CLIA-certified assays (e.g., Guardant360) are permitted to be shared with patients and their treating physicians. Because the results generated by other genetic testing included in this section are not currently anticipated to have clinical relevance to the patient or their family members, the genetic results will not be disclosed to the patients or their physicians.

If at any time, genetic results are obtained that may have clinical relevance, IRB review and approval will be sought regarding the most appropriate manner of disclosure and whether or not validation in a CLIA-certified setting will be required. Sharing of research data with individual patients should only occur when

data have been validated by multiple studies and testing has been done in CLIA-approved laboratories.

15.0 Drug Information

IND exempt

- Investigator brochure
Will be sent hard copy to sites by ACCRU. Sites will email Research Protocol Specialist with shipping address.

15.1 Panitumumab (Vectibix®)

15.11 **Background:** Panitumumab is a recombinant human IgG2 monoclonal antibody which binds specifically to the epidermal growth factor receptor (EGFR, HER1, c-ErbB-1) and competitively inhibits the binding of epidermal growth factor (EGF) and other ligands. Binding to the EGFR blocks phosphorylation and activation of intracellular tyrosine kinases, resulting in inhibition of cell survival, growth, proliferation and transformation. EGFR signal transduction results in KRAS wild-type activation; cells with KRAS mutations appear to be unaffected by EGFR inhibition.

15.12 **Formulation:** Panitumumab is supplied as a sterile, colorless, preservative-free solution in a single-dose vial. The vial is designed to deliver 20 mg/mL (5 mL, 20 mL).

15.13 **Preparation, storage, and stability:** Store unopened vials at refrigerated temperature 2 to 8°C (36° to 46°F), do not freeze or shake, protect from light. Dilute in 100-150 mL of 0.9% sodium chloride injection, USP to a final concentration of less than or equal to 10 mg/mL. Doses higher than 1000 mg should be diluted to 150 mL with 0.9% sodium chloride injection, USP. Do not shake, invert gently to mix. Preparations in infusion containers are stable for 24 hours under refrigeration (2° to 8°C or 36° to 46°F) or for 6 hours at room temperature. Do not freeze the diluted solution.

15.14 **Administration:** Doses less than or equal to 1000 mg, infuse over 1 hour; doses > 1000 mg, infuse over 90 minutes. For doses that are less than or equal to 1000 mg, if the first infusion is well tolerated, subsequent infusions may be administered over 30 to 60 minutes. Reduce infusion rate by 50% for mild-to-moderate infusion reactions (grades 1 and 2); discontinue for severe infusion reactions (grades 3 and 4). Administer through a low protein-binding 0.2 or 0.22 micrometer in-line filter. Flush with 0.9% sodium chloride injection, USP before and after infusion.

15.15 **Pharmacokinetic information:**
Half-life elimination: ~7.5 days (range: 3.6 to 10.9 days)

15.16 **Potential Drug Interactions:**
Increased Effect/Toxicity: There are no known interactions where it is recommended to avoid concomitant use.

15.17 Known potential adverse events:**Most common known potential toxicities, > 10%:**

General disorders: Fatigue/asthenia, pyrexia, mucosal inflammation, peripheral edema, weight loss, decreased appetite

Dermatologic: Skin toxicity, erythema, pruritus, dry skin, dermatitis acneiform, paronychia, rash, skin fissure, acne, conjunctivitis, alopecia

Endocrine & metabolic: Hypomagnesemia, hypokalemia

Gastrointestinal: Nausea, diarrhea, constipation, vomiting, abdominal pain, stomatitis

Respiratory: Dyspnea, cough

Musculoskeletal: Back pain

Nervous system disorder: Paresthesia

Psychiatric: Insomnia

Common known potential toxicities, 1% - 10%:

Cardiovascular: Pulmonary embolism, epistaxis, deep vein thrombosis, flushing

Central nervous system: Chills, headache, dizziness

Dermatologic: Exfoliative rash, nail disorder, skin exfoliation, palmar-plantar erythrodysesthesia syndrome, hyperhidrosis, macular rash, hypertrichosis, maculopapular rash, skin toxicity, onychoclasia pruritic rash, abnormal hair growth, pain of the skin, skin lesion, dermatitis, generalized rash

Endocrine & metabolic: Dehydration, decreased blood magnesium, hypocalcemia, hyperglycemia, hyperphosphatemia

Gastrointestinal: Dyspepsia, dry mouth, rectal hemorrhage, gastroesophageal reflux disease, lower abdominal pain, aphthous ulcer, oral pain, cheilitis

Immunologic: Hypersensitivity

Ocular: Increased lacrimation, dry eye, abnormal eyelash growth, blepharitis, ocular hyperemia, eye irritation, eye pruritus

Hematologic: Leukopenia

Infections and infestations: Urinary tract infection, pustular rash, folliculitis, cellulitis, localized infection

Musculoskeletal: Pain in extremity

Psychiatric: Anxiety

Uncommon known potential toxicities, <1%

Eye disorders: Eyelid irritation, keratitis, ulcerative colitis

Gastrointestinal: Chapped lips, dry lip

Infections and infestations: Eye infection, nail infection, eyelid infection

Procedural complication: Infusion related reaction

Nervous system disorder: Cholinergic syndrome

Respiratory, thoracic and mediastinal disorders: Nasal dryness

Skin and subcutaneous tissue: Ingrowing nail, onycholysis, hirsutism, angioedema, skin necrosis, Stevens-Johnson syndrome/toxic epidermal necrolysis,

Immunologic: Hypersensitivity reaction

Respiratory: Interstitial lung disease

15.18 **Drug procurement:** Each participating ACCRU treating location will fill out the pharmacy contact sheet posted in ARMS. ACCRU will send sites a site specific Drug Order Form. Sites will then send completed Drug Order Form to email address listed on the form.

Each participating ACCRU treating location will be responsible for monitoring the supply of panitumumab and will use the Drug Order Request Form to order additional supplies as needed.

Outdated or remaining drug is to be destroyed on-site as per procedures in place at each institution.

15.19a Temperature excursions that occur at the site should be reported by the site using the Temperature Excursion Form found on the ACCRU web site for this study and emailed to 'send to' address on the form.

15.19b Nursing Guidelines:

15.19b1 Patient may experience typical EGFR inhibitor related rash, which is generally acneiform in nature and may be associated with pruritis and erythema. Treat symptomatically and monitor for effectiveness.

15.19b2 Premedication is generally not required with panitumumab administrations as infusion related reactions are rare. If patients do experience a transfusion related reaction, stop the infusion, inform the MD and treat as necessary. Patient then may need premedication prior to future infusions.

15.19b3 Panitumumab must be infused via infusion pump through a 0.2 or 0.22 micron in-line filter infusion set up. Flush with 0.9% sodium chloride injection, USP before and after infusion.

15.19b4 Hypomagnesemia is seen with this agent. Monitor magnesium level prior to each infusion. If level is below normal, inform the MD.

15.19b5 Patients may experience nail related changes, including discoloration, ridging, paronychias, and/or loss of the nail itself. Instruct patients to report nail changes to the study team, as intervention may be indicated.

15.19b6 Gastrointestinal side effects including nausea, diarrhea, constipation and vomiting have been seen. Treat symptomatically and monitor for effectiveness.

15.19b7 Monitor patients closely and instruct them to report any side effects to the study team as all side effects of panitumumab in combination with chemotherapy are not known at this time.

15.19b8 Panitumumab is a protein and should be handled carefully to

avoid break down of the product. This includes both when mixing from the vial and when administering the product via IV infusion.

15.2 **Regorafenib (BAY 73-4506, Stivarga®)**

- Refer to package insert for complete, up-to-date information.

15.21 **Background**

Regorafenib is a novel oral multi-kinase inhibitor that targets tumor cells and the tumor microenvironment. It inhibits tumor growth, progression and metastasis by inhibiting the proliferation of tumor cells, the formation of new tumor vasculature and stromal signaling in the microenvironment of the tumor.

15.22 **Formulation**

Commercially available as light pink, oval-shaped 40 mg tablets. Tablets are supplied in packages containing three bottles, with each bottle containing 28 tablets.

15.23 **Preparation and storage**

Once the drug has been received it must be kept in a secure, dry location. Study drug must be stored in its original bottle at a temperature not above 25°C (77°F).

15.24 **Administration**

Regorafenib tablets should be taken in the morning with approximately 8 fluid ounces (240 mL) of water after a low-fat (<30% fat) breakfast. Regorafenib should not be taken with grapefruit juice.

15.25 **Pharmacokinetic information**

- a) Absorption – Following a single 160 mg dose of Regorafenib in patients with advanced solid tumors, regorafenib reaches a geometric mean peak plasma level (C_{max}) of 2.5 μ g/mL at a median time of 4 hours and a geometric mean area under the plasma concentration vs time curve (AUC) of 70.4 μ g*h/mL. A high-fat meal increased the mean AUC of the parent drug by 48% compared to the fasted state and decreased the mean AUC of the M-2 (N-oxide) and M-5 (N-oxide and N-desmethyl) active metabolites by 20% and 51%, respectively. A low-fat meal increased the mean AUC of regorafenib, M-2 and M-5 by 36%, 40% and 23%, respectively (as compared to the fasted state).
- b) Distribution – Regorafenib undergoes enterohepatic circulation with multiple plasma concentration peaks observed across the 24-hour dosing interval. Regorafenib is highly bound (99.5%) to human plasma proteins.

- c) Metabolism – Regorafenib is metabolized by CYP3A4 and UGT1A9. The main circulating metabolites measured at steady state are M-2 (N-oxide) and M-5 (N-oxide and N-desmethyl), both of them having similar *in vitro* pharmacological activity and steady-state concentrations as regorafenib. M-2 and M-5 are highly protein bound (99.8% and 99.95%, respectively).
- d) Elimination – Elimination half-lives for regorafenib and the M-2 metabolite in plasma are 28 hours (14 to 58 hours) and 25 hours (14 to 32 hours), respectively. M-5 has a longer mean (range) elimination half-life of 51 hours (32 to 70 hours).
- e) Excretion – Approximately 71% of radiolabeled dose was excreted in feces (47% as parent compound; 24% as metabolites); and 19% of the dose was excreted in urine (17% as glucuronides).

15.26 Potential Drug Interactions

Avoid concomitant use of strong CYP3A4 inducers (i.e. rifampin, phenytoin, carbamazepine, phenobarbital and St. John's Wort) and strong CYP3A4 inhibitors (i.e. clarithromycin, grapefruit juice, itraconazole, ketoconazole, nefazodone, posaconazole, telithromycin and voriconazole).

Co-administration of Regorafenib with a Breast Cancer Resistance Protein (BCRP) substrate increased the plasma concentrations of the BCRP substrate. Monitor patients closely for signs and symptoms of exposure related toxicity to the BCRP substrate (e.g. methotrexate, fluvastatin, atorvastatin).

15.27 Known potential toxicities

Consult the package insert for the most current and complete information.

Serious Adverse Effects

Hepatotoxicity: [U.S. Boxed Warning]: Severe liver toxicity and hepatic failure (sometimes resulting in death) have been observed in clinical trials; hepatocyte necrosis with lymphocyte infiltration has been demonstrated with liver biopsy. Monitor hepatic function at baseline and during treatment. Interrupt therapy for hepatotoxicity; dose reductions or discontinuation are necessary depending on the severity and persistence.

Most Common Adverse Events, >10%:

Cardiovascular: Hypertension, hemorrhage

Central nervous system: Fatigue, dysphonia, pain, fever, headache.

Dermatologic: Skin toxicity, Palmar-plantar erythrodysesthesia, rash

Endocrine & metabolic: Hypocalcemia, hypophosphatemia, hyponatremia, hypokalemia

Gastrointestinal: Appetite decreased, lipase increased, diarrhea, mucositis, weight loss, amylase increased

Hematologic: Anemia, lymphopenia, thrombocytopenia, INR increased, neutropenia

Hepatic: AST increased, ALT increased, hyperbilirubinemia

Renal: Proteinuria

Miscellaneous: Infection, pain (including gastrointestinal and abdominal pain)

Less Common Adverse Events, 1% - 10%:

Hepatic: Hepatic failure

Rare Adverse Events (Important or life-threatening), <1%:

Gastrointestinal: Gastrointestinal perforation, gastrointestinal fistula,

Cardiovascular: Cardiac ischemia or infarction

Neurologic: Reversible posterior leukoencephalopathy syndrome (RPLS)

Dermatologic: Stevens-Johnson syndrome, toxic epidermal necrolysis

Additional risks:

Hypersensitivity reactions: Hypersensitivity reactions have been reported during post-approval use of regorafenib. Because these reactions are reported voluntarily from a population of uncertain size, it is not always possible to reliably estimate their frequency or establish a causal relationship to drug exposure

Wound Healing Complications: No formal studies of the effect of regorafenib on wound healing have been conducted. Since vascular endothelial growth factor receptor (VEGFR) inhibitors such as regorafenib can impair wound healing, discontinue treatment with regorafenib at least 2 weeks prior to scheduled surgery. The decision to resume regorafenib after surgery should be based on clinical judgment of adequate wound healing. Discontinue regorafenib in patients with wound dehiscence.

Embryo-Fetal Toxicity: Based on animal studies and its mechanism of action, regorafenib can cause fetal harm when administered to a pregnant woman. There are no available data on regorafenib use in pregnant women. Regorafenib was embryolethal and teratogenic in rats and rabbits at exposures lower than human exposures at the recommended dose, with increased incidences of cardiovascular, genitourinary, and skeletal malformations. Advise pregnant women of the potential risk to a fetus. Advise females of reproductive potential to use effective contraception during treatment with regorafenib and for 2 months after the final dose. Advise males with female partners of reproductive potential to use effective contraception during treatment with regorafenib and for 2 months after the final dose.

15.28 **Drug procurement:** Commercial supplies. Each participating ACCRU treating location shall obtain supplies from normal commercial supply chain or wholesaler.

Outdated or remaining drug is to be destroyed on-site as per procedures in place at each institution.

15.29 **Nursing Guidelines**

15.291 Liver toxicity and liver failure have resulted from this agent. Monitor LFT's closely and instruct patients to report any abdominal pain, jaundice or significant fatigue to the study team. Dose reduce or interrupt treatment as per protocol.

15.292 Hypertension has been seen. Monitor blood pressure as outlined in protocol.

15.293 Instruct patient to report a rash, or signs and symptoms of palmar-plantar erythrodysesthesia to the study team. Rarely SJS and TENS have been seen with this agent. Instruct patients to seek immediate medical attention if they experience rash with fever, blisters, sloughing of tissue (especially in the mouth and vaginal, anal regions). Treat symptomatically and monitor for effectiveness.

15.294 Inform patients of possibility of alopecia.

15.295 Gastrointestinal side effects can include, diarrhea, nausea, vomiting, decreased appetite, weight loss, mucositis and less commonly taste changes, dry mouth, and reflux. Treat symptomatically and monitor for effectiveness.

15.296 Cytopenias are seen with agent. Monitor CBC w/diff and instruct patient to report signs, symptoms of infection or any unusual bruising or bleeding to the study team.

15.297 Secondary skin cancers have been reported. Instruct patients to report new or changing lesions to study team.

15.298 Reversible Posterior Leukoencephalopathy Syndrome (RPLS) is a rare (<1%) but serious condition. Presenting symptoms may include changes in mental status, visual disturbance, seizure, or other CNS changes. Patients with this syndrome generally had HTN as well, therefore BP monitoring is important. Instruct patient to report any mental status changes, visual changes, seizures, or other CNS changes to the MD immediately. These may be a sign of RPLS or more serious condition, such as hemorrhagic event in the CNS.

15.3 **TAS-102 Trifluridine (FTD)/Tipiracil (TPI) (TAS-102, Lonsurf®)**

- Refer to package insert for complete, up-to-date information.

15.31 **Background**

TAS-102 is a combination of trifluridine, a nucleoside metabolic inhibitor, and tipiracil, a thymidine phosphorylase inhibitor, indicated for the treatment of patients with metastatic colorectal cancer who have been previously treated with fluoropyrimidine-, oxaliplatin- and irinotecan-based chemotherapy, an anti-VEGF biological therapy, and if RAS wild-type, an anti-EGFR therapy

15.32 **Formulation**

- FTD/TPI (TAS-102) tablet (15 mg) contains 15 mg trifluridine and 6.14 mg tipiracil as active ingredients. The appearance is white round tablet.
- FTD/TPI (TAS-102) tablet (20 mg) contains 20 mg trifluridine and 8.19 mg tipiracil as active ingredients. The appearance is pale red round tablet.

15.33 **Preparation and storage**

Store at 20°C to 25°C (68°F to 77°F); excursions are permitted from 15°C to 30°C (59°F to 86°F). If stored outside of original bottle, discard after 30 days. TAS-102 is a cytotoxic drug. Follow applicable special handling and disposal procedures.

15.34 **Administration**

Recommended to take within 1 hour after completion of the morning and evening meals. Anyone other than the patient who handles their medication should wear gloves.

15.35 **Pharmacokinetic information**

After twice daily dosing of TAS-102, systemic exposure (AUC) of trifluridine increased more than dose-proportionally over the dose range of 15 to 35 mg/m². After administration of TAS-102 35 mg/m² twice daily, the mean elimination half-life (t_{1/2}) of trifluridine was 1.4 hours and of tipiracil was 2.1 hours after a single dose. The mean elimination half-life at steady state of trifluridine was 2.1 hours and of tipiracil was 2.4 hours.

Protein Binding

Trifluridine: >96% (primarily to albumin); Tipiracil: <8%

Metabolism

Trifluridine and tipiracil are not metabolized by cytochrome P450 (CYP) enzymes. Trifluridine is mainly eliminated by metabolism via thymidine phosphorylase to form an inactive metabolite, 5-(trifluoromethyl) uracil (FTY)

Excretion

Following a single dose of TAS-102, the mean 48-hour cumulative urinary

excretion was 1/5% for unchanged trifluridine, 19.2% for FTY, and 29.3% for unchanged tipiracil.

15.36 Potential Drug Interactions

Trifluridine is a substrate of thymidine phosphorylase, and is not metabolized by cytochrome P450 (CYP) enzyme. Tipiracil is not metabolized in either human liver or hepatocytes.

In vitro studies indicated that trifluridine, tipiracil, and FTY did not inhibit the CYP enzymes and had no inductive effect on CYP1A2, CYP2B6, or CYP3A4/5.

In vitro studies indicated that trifluridine was not an inhibitor of or substrate for human uptake and efflux transporters.

15.37 Known potential toxicities

Consult the package insert for the most current and complete information.

Most common known potential toxicities, >/= 10%:

Blood and lymphatic: Anemia, neutropenia, thrombocytopenia

Gastrointestinal: Diarrhea, nausea, vomiting, abdominal pain

General: Fatigue, pyrexia, infection

Metabolism and nutrition: Decreased appetite

Common known potential toxicities, >/=1% - <10%:

Cardiovascular: Pulmonary emboli

Gastrointestinal: Stomatitis

Nervous System: Dysgeusia

Uncommon known potential toxicities, <1% (Limited to important or life-threatening):

Blood and lymphatic: Severe myelosuppression

Respiratory: Interstitial lung disease

15.38 Drug procurement: Commercial supplies. Each participating ACCRU treating location shall obtain supplies from normal commercial supply chain or wholesaler.

Outdated or remaining drug is to be destroyed on-site as per procedures in place at each institution.

15.39 Nursing Guidelines

15.391 Instruct patients that agent should be taken within 1 hour after completion of morning and evening meal.

15.392 Patients may experience fatigue. Instruct patients in energy conserving lifestyle.

15.393 GI side effects are common, including nausea, decreased appetite,

diarrhea, vomiting, and abdominal pain.

15.394 Cytopenias are common. Monitor CBC w/diff and instruct patients to report any signs or symptoms of infection and/or unusual bruising or bleeding to the study team.

15.395 Rarely Pulmonary embolism has been reported with this agent. Instruct patient to report any shortness of breath or chest pain to study team and/or seek out emergency medical attention.

15.396 Although uncommon, inform patients of the possibility of alopecia.

16.0 Statistical Considerations and Methodology

16.1 Overview and Study Design

This is a randomized Phase II study which is designed to compare the overall survival (OS) in patients with EGFR refractory *RAS* wild-type metastatic CRC, who are randomized to panitumumab or standard therapy (TAS-102 or regorafenib). Prior studies have shown that the median OS is around 6.5 months for patients in this disease population receiving TAS-102 or regorafenib and PFS is around 1.9 months for patients receiving TAS-102 or regorafenib in this disease population [40, 41]. It is hypothesized that panitumumab can increase the median OS to at least 10 months. In addition to OS, this trial will also compare the overall response rate, PFS, adverse event rates, and self-reported quality of life outcomes (measured by LASA) between the panitumumab arm and standard therapy (TAS-102 or regorafenib).

16.11 Primary Endpoint

The primary endpoint for this study is overall survival (OS) which is defined as the time from randomization to death from any cause. Patients who are alive will be censored at the last known alive date.

16.12 Interim Analysis

One interim analysis for futility will be conducted when at least 42 patients across both arms combined have provided documentation of death. Overall survival will be used as the endpoint for the interim analysis. The interim futility boundary was selected using EAST software. Un-stratified log-rank p-value will be used for decision making. The trial will continue accrual while the interim analysis is being conducted. If the 1-sided p-value > 0.529 for panitumumab compared to standard therapy (TAS-102 or regorafenib), which corresponds to a hazard ratio (HR) > 1.022 , the panitumumab will be considered as futile and the accrual will be suspended. Otherwise, if the 1-sided p-value ≤ 0.529 (HR ≤ 1.022), the study will continue to full accrual and the final analysis will be conducted as described below.

16.13 Final Analysis

Efficacy analysis will be conducted when at least 83 death events, across

both arms combined, have been observed. The stratified log-rank test will be used for decision making except when there are 0 events in any of the strata; in that case, the un-stratified log-rank will be used for decision making. If the 1-sided p-value is > 0.15 for panitumumab compared to standard therapy (TAS-102 or regorafenib), which corresponds to a hazard ratio (HR) > 0.797 , panitumumab will be considered as ineffectual; if the 1-sided p-value ≤ 0.15 (equivalently, HR ≤ 0.797), panitumumab will be considered as promising for future study. All eligible patients who sign the consent form, are randomized, and received any protocol treatment are considered evaluable for this endpoint.

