- 6 Receipt of archival tumor tissue is not required for study randomization and initiation of therapy. However, it is mandatory to receive the required tissue within 90 days from randomization. See section 17.0.
- 7 Patients have the option to complete cfDNA testing at study completion and will be allowed to re-register with protocol ACCRU-GI-1611. Site will access results by creating an account at [REDACTED] Sites will be notified by Guardant Health via email when results are available in the portal. Refer to Section 13.7. See detailed instructions on the ACCRU website under Manuals and Forms.
- 8 May discontinue day 15 visit beginning cycle 7. Additional visits and laboratory studies are permitted as per institutional practice and as clinically appropriate.
- 9 Patient must be registered prior to collection.
- 10 Patient questionnaire will be completed at baseline and each cycle (Appendix II). Patient questionnaire booklets **must** be used; copies are not acceptable for this submission. The booklet order form is located on the ACCRU website under Manuals and Forms.
- 11 If screening tests occur ≤ 7 days prior to C1D1, they do not have to be repeated prior to dosing.
- 12 The COLOMATE Companion Trial Recommendation Form must indicate that the patient has met molecular eligibility to screen. The patient must be registered to the companion study ≤30 days from date of COLOMATE Companion Trial Recommendation Form completion. If the COLOMATE Companion Trial Recommendation Form recommends a different companion study, patient may still enroll.
- 13 The diary must begin the day the patient starts taking the medication and must be completed per protocol and returned to the treating institution OR compliance must be documented in the medical record by any member of the care team.

R Research funded.

Event Monitoring: survival follow-up will be done every 3 months (± 7 days) until 3 year after randomization.

5.0 Stratification Factors:

- 5.1 Primary tumor location: right (cecum, ascending colon, hepatic flexure, and transverse colon) vs left (splenic flexure, descending colon, sigmoid colon, rectosigmoid junction, and rectum).
- 5.2 Prior TAS-102 or regorafenib: Yes vs No.

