6.2 Randomization Procedures

- 6.21 The factors defined in Section 5.0, together with the registering membership, will be used as stratification factors.
- 6.22 After the patient has been registered into the study, the values of the stratification factors will be recorded, and the patient will be assigned to

one of the following treatment groups using the Pocock and Simon [39] dynamic allocation procedure which balances the marginal distributions of the stratification factors between the treatment groups.

- Panitumumab
- Standard Therapy (regorafenib or TAS-102)

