16.15 Power and Sample Size

The primary goal is to compare the OS between patients who are randomized to panitumumab and those randomized to standard therapy (TAS-102 or regorafenib). The null hypothesis is that the panitumumab arm does not show a superior OS outcome compared to standard therapy (TAS-102 or regorafenib). The alternative hypothesis is that the panitumumab arm has improvement in OS compared to standard therapy (TAS-102 or regorafenib).

We will enter 53 evaluable patients to each arm of the study using a 1:1 randomization scheme (106 evaluable patients in total); unless the study is stopped early. Stratification factors are defined in section 5.0. With 53 evaluable patients per arm, we have 80% power to detect an improvement in the median OS from 6.5 to 10 months (HR=0.65), assuming a 1-sided significance level of 0.15 and an accrual rate of 8 patients per month. The trial has a single interim analysis for futility, adopting the Rho family (Rho=1.5) beta spending function for controlling the overall type II error rate and will be considered non-binding.

16.151 Operating Characteristics

The table below shows the operating characteristics assuming the OS follows the exponential survival function along with a one-sided significance level of 0.15.

The table below includes the operating characteristics according to the monitoring plan outlined above. The proportion of times that 1) the study would stop early at the interim analysis due to futility of panitumumab, and 2) the study would conclude panitumumab is superior to TAS-102 or regorafenib at the final analysis, are tabulated by true OS median survival times and equivalent true

hazard ratios for OS by treatment groups.

True median overall survival (months) ¹		True Hazard Ratio	% of times the study will be stopped for futility at the interim analysis ²	% of times that panitumumab is deemed superior at the final analysis ²
TAS-102 or regorafenib	panitumumab			
6.5	6.5	1	47.7	14.1
6.5	7.2	0.90	34.3	26.8
6.5	7.9	0.82	24.3	41.9
6.5	8.6	0.76	16.5	56.7
6.5	9.3	0.70	11.2	69.9
6.5	10	0.65	7.5	79.4

¹ Although we use the median OS to illustrate each scenario, the hypothesis testing is based on the entire survival curve.

² Proportions are based on 50,000 replicates in a simulation study

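### Does the zero-event exception in Section 16.13, where the strata are not named, put the final overall survival test at risk?

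*Combined protocol and SAP*

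**What the plan says.** Section 16.13 sets the final decision test: "The stratified log-rank test will be used for decision making except when there are 0 events in any of the strata", and "in that case, the un-stratified log-rank will be used for decision making". The threshold is a one-sided p-value of 0.15 at 83 deaths. Section 16.13 does not list the strata.

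Section 16.15, which gives the power for the same comparison, says "Stratification factors are defined in section 5.0". Section 5.0 lists two factors, each with two levels: "Primary tumor location: right (cecum, ascending colon, hepatic flexure, and transverse colon) vs left" and "Prior TAS-102 or regorafenib: Yes vs No".

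Section 6.21, under the randomization procedures, says "The factors defined in Section 5.0, together with the registering membership, will be used as stratification factors". Section 6.22 then describes a Pocock-Simon "dynamic allocation procedure which balances the marginal distributions of the stratification factors between the treatment groups".

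For the interim futility look, Section 16.12 says "Un-stratified log-rank p-value will be used for decision making".

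**The concern.** Two features look wrong on a first reading.

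The first is the exception itself. The stratified log-rank test can be computed when a stratum has no deaths, so there is no technical reason to abandon it. Yet a single such stratum removes the stratification from the whole go/no-go test, and which test decides then depends on the observed data. It is also unclear whether a cell with no patients counts as a stratum with 0 events.

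The second is that how often the exception fires depends on what the strata are. Section 5.0 gives four cells. If membership, named in 6.21, were crossed in, there would be four cells per membership, many of them tiny, and the allocation balances only the margins. The exception would then often replace the planned test. If it were removed on that reading, the test would run on sparse cells and lose power. A dispute after the data are known about which test was intended would be serious, because the trial's conclusion rests on one p-value.

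**Working it through.** **1. The plan's own figures.** With 83 deaths, 1:1 allocation and one-sided alpha 0.15 (z = 1.036):
- Critical hazard ratio (HR): exp(-2 × 1.036/√83) = 0.797. The plan states 0.797.
- Power at HR 0.65 without the interim look: Φ(√83/2 × 0.4308 - 1.036) = Φ(0.926) = 82.3%. With the futility look at 42 deaths it is 80.3%; the plan states 80%, and 79.4% in its table.

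The design figures hold and are not in question.

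**2. A stratum with no deaths.** The stratified statistic is U²/V. Here U sums (deaths observed minus expected in one arm), and V sums the hypergeometric variances, over all death times in all strata. A stratum without death times adds an empty sum, 0, to each. A numerical check agrees: adding a six-patient stratum with no deaths to a three-stratum data set left chi-square at 0.53856 and p at 0.46303. The exception is therefore unnecessary for computing the test.

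**3. Which strata.** Section 16.15 is in the statistics section, concerns the same comparison, and points to Section 5.0 alone. Section 6.21 governs allocation and adds membership to the Section 5.0 list for that purpose. An analyst would use the four Section 5.0 cells.

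**4. How often the exception fires with four cells.** Inputs: 106 evaluable patients and 83 deaths (Sections 16.15 and 16.13). The prevalences are assumptions; the documents give none. Let q be the share of patients in the smallest cell, with factors independent and not prognostic. Then:
- P(no deaths in that cell, empty cell counted) = (1 - q × 83/106)^106
- P(cell empty) = (1 - q)^106
- P(no deaths in an occupied cell) = the difference

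| Right-sided / prior drug | q | Empty cell counted | Cell empty | Occupied cell only |
|---|---|---|---|---|
| 20% / 30% | 0.06 | 0.6% | 0.1% | 0.5% |
| 20% / 20% | 0.04 | 3.4% | 1.3% | 2.1% |
| 10% / 25% | 0.025 | 12.3% | 6.8% | 5.5% |
| 10% / 10% | 0.01 | 43.5% | 34.5% | 9.0% |

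The other three cells add almost nothing.

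**5. What the exception changes.** The relevant comparison is the written rule against an always-stratified two-factor test. The simulations used exponential survival, 106 patients and final analysis at the 83rd death, without the interim look.
- Type I error and power differ by less than 0.5 percentage points in every scenario. At 10%/10% with no prognostic effect and empty cells counted, type I error is 0.154 (rule) against 0.153, and power 0.816 against 0.813.
- Verdicts differ in 0.00-0.04% of trials at 20%/30%. At 20%/20% the figure is 0.06%, or 0.14% with empty cells counted. At 10%/25% it is about 0.3-0.6%. At 10%/10% it is 0.3-0.5%, or 1.0-1.8% with empty cells counted.

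These sizes are plausible by hand. The two tests, each used always, give opposite verdicts in 3.5-7.4% of trials. At 20%/30% the exception fires in 0.6%, and 0.006 × 0.074 = 0.04%. At 10%/10%, 0.435 × 0.035 = 1.5%.

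**6. The membership reading, for comparison.** At 20%/30% with 5, 10 or 20 memberships (assumed), the exception would fire in 54%, 92% and over 99% of trials if the factors are not prognostic. If right side carries HR 2.0 and prior drug HR 1.5, it would fire in 17%, 63% and 98%. Power under the written rule would be 76-82%. The fully crossed stratified test would have about 74%, 68-69% and 59%, and the two-factor test 80-81%. Null rejection by the written rule stays at 0.148-0.155.

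**The case for a change.** The strongest case for a change is that it is cheap and the deciding test ought to be beyond dispute. The exception is a poor safeguard against sparse data: it ignores a stratum with one death, or with deaths but only one arm at risk, yet reacts to an empty one. Stratified and unstratified tests give opposite verdicts in 3.5-7.4% of simulated trials, so which one is used can matter. On the membership reading the written rule disagrees with the two-factor test in 4-11% of trials.

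Part of this stands. The exception serves no purpose with four strata, the status of an empty cell is not stated, and 16.13 would be clearer with the cross-reference repeated.

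The figures do not carry the rest. The 3.5-7.4% compares two tests each applied always, while the plan applies the stratified test and switches only when the exception fires. The 4-11% needs a reading that 16.15 does not support. Even there the exception helps: the rule keeps power at 76-82% where the crossed test would fall to 59-74%. Deleting the exception alone would remove that protection.

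**Conclusion.** No change to the plan follows. The exception is superfluous, and the unnamed strata in 16.13 are a gap that analysts fill sensibly from 16.15 and Section 5.0. On that four-cell reading, following the plan as written changes type I error and power by less than 0.5 percentage points, with no consistent direction, and alters the verdict in about 0-2% of trials. Removing the exception therefore shows no reliable gain. Validity is not affected: the rule is pre-specified, it is triggered by event counts pooled over arms, and simulated type I error is consistent with 0.15. The 83 deaths and 80% power stand.

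The conclusion rests on Section 5.0 defining the analysis strata and on the prevalences being in the assumed range. The upper end, near 2%, needs a cell holding about 1% of patients and an empty cell counted as a stratum. The simulations leave out the interim look, which uses the unstratified test on either version.
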